In Session 1 (pre-medication baseline), we will collect baseline measures of smoking urge, withdrawal symptoms, mood, cognitive performance, a behavioral economics-based measure of cigarette demand and effects of smoking a cigarette on cigarette reward, satisfaction and mood. Next, participants will be randomized to VAR (1 mg twice daily for 3 weeks) or PLA, using urn randomization to stratify on gender and dependence. Participants will complete a week of medication use using the standard dose run-up (0.5 mg once daily on days 1-3, 0.5 mg twice daily on days 4-7, then 1 mg twice daily until the end of the medication period). In Session 2, which occurs after one week on medication, participants will complete the same laboratory assessments as in Session 1. Next, participants will undergo a 3-day abstinence period. They will come to the laboratory twice per day and will receive escalating cash incentives for breath carbon monoxide (CO)-verified abstinence. At each visit, cigarette craving and withdrawal symptoms will be measured. At Session 8 (Thursday morning), participants who have been continuously abstinent will complete the same procedure as in Sessions 1. For ethical reasons, participants who complete the study through Thursday and who wish to remain abstinent may opt out of smoking during this session and will still receive full compensation for participation, as long as they attend this lab session and complete the other session measures.

Participants will be asked to return to the laboratory on Friday morning. Breath CO will be measured and time of first lapse (single cigarette) and relapse (return to regular smoking) will be collected among those who have lapsed and relapsed. Those still abstinent ($CO \leq 4$ ppm) since Session 8 will receive a small cash incentive. Next, participants will be shown how to use breath CO monitors with smart phones to record

and text us videos of themselves providing CO samples twice per day for the following week to determine time to lapse and relapse. Participants will receive \$5 for each submitted sample (not contingent on CO level), paid when the smart phone and CO monitor are returned at the end of the week.

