It will be made clear to participants that all information obtained during assessments is confidential and that no information will be shared with the participants' clinicians unless the participant requests this in writing. All investigators and staff associated with this project have been trained, and new hires will be trained, on human research ethics in accordance with the requirements of the local institutions during initial project approval.

The PI will train and closely monitor the Research Assistant on the procedures to be used in this study. Such monitoring will consist of frequent in-person discussion of study visits at the beginning of the study and less frequent monitoring as the study progresses. The PI and Research Assistant will meet at least weekly to discuss any study issues and their resolution.

Questionnaires administered during the screening interview will be read to participants and filled out by the Research Assistant, to maximize accuracy and completeness of these data. After enrollment, questionnaires that are administered at repeated time points during the study (e.g., QSU) will be completed by participants. The first time that participants complete these questionnaires, the Research Assistant will go over the questionnaires to ensure that participants understand the questions. Subsequently, the Research Assistant review the questionnaire instructions with participants and will be available to the participant to answer any questions he/she may have. Questionnaires will be reviewed for completeness while the participant is present. On computerized forms or tasks, participants cannot accidentally skip a question, but may choose not to answer questions. Biochemical measures (expired breath CO, urine pregnancy, urine drug) will be analyzed immediately, while the participant is present. If necessary (e.g., if the sample volume is insufficient for analysis), the Research Assistant can gather another sample immediately and re-analyze.

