Standard operating procedures and case report form templates will be developed to ensure that data are collected consistently during the study. Each visit will have a checklist of all measures that need to be obtained and the order in which these measures are to be administered. Once a participant has completed all study procedures and all open events have been closed, the PI will review the participant's binder and sign a form indicating study completion for that participant. Oversight of the study and adherence to protocol procedures will be conducted by the PI or another study staff member (e.g., post-doctoral fellow) who has been trained and is supervised by the PI.

VAR and matching PLA will be prepared by a pharmacist by compounding VAR tablets or placebo lactose powder to capsules that are identical in appearance. The standard VAR dosing will be used: 0.5 mg/day on days 1–3, 0.5 mg twice daily (morning, evening) on days 4–7, then 1 mg twice daily to the end of the medication period. VAR and PLA will be distributed in identical 7-day medication blister packs, marked with the participant’s study identification number and letter code.

A medication randomization table will be created by the PI. The Research Assistant will be provided with a copy that has letter codes (A, B, C, or D) instead of medication names. When the Research Assistant enrolls a participant, the Research Assistant will enter the participant’s name and ID number on a row the table, note the medication letter code for that row on the participant’s enrollment form, and take the medication pack with that letter code. The Research Assistant will then provide the Data Manager with a copy of the randomization table so that the data manager can update his records.

[name] will remain blind to medication condition during each phase (R21 phase, R33 phase). The Data Manager will break the blind for [name] at the end of each phase. The Data Manager will break the blind for the medical monitor ([name]) in case of adverse events requiring medical intervention.

Regulatory Issues

Reporting of SAEs

Serious events as defined in 21 CFR 312.32 will be reported to the Brown University IRB, the NIDA Project Officer, and the DSMB. The Brown University IRB requires that fatalities and all other SAEs related to the study products be reported within 5 days of receiving notice of the event. SAEs related to the study will be reported to NIDA within 72 hours.

Reporting of IRB actions to NIDA

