
- 4) Nicotine Withdrawal: Participants may experience some discomfort when abstaining from smoking. Symptoms can include irritability, frustration, anxiety, depressed mood or sadness, desire or craving to smoke, difficulty concentrating, and increased appetite or hunger. These feelings can be uncomfortable but they are normal, temporary, and usually mild.
- 5) Effects of Varenicline (VAR): The results of the largest study to date of varenicline's efficacy and safety in smokers with and without psychiatric disorders found no increase in neuropsychiatric adverse events attributable to varenicline relative to nicotine patch or placebo (Anthenellie et al., 2016). The most frequent adverse event associated with varenicline is mild to moderate nausea, occurring in 25-45% of users, diminishing over time, and not leading to varenicline discontinuation (Anthenelli et al., 2016; Cahill et al., 2009; Ebbert et al., 2010; Evins et al., 2014; Leung et al., 2011). Other common adverse events include insomnia, abnormal dreams and headaches; serious adverse events have been rare in randomized, controlled phase III studies, and there have been no treatment-related deaths and no known contraindications (Anthenelli et al., 2016; Aubin et al., 2014; Evins et al., 2014). Nevertheless, patients receiving VAR should and will be monitored in this study for changes in psychiatric symptoms including mood and suicidality. Co-Investigators [name], a licensed clinical psychologist, and [name], an addictions psychiatrist, will assess and assist with any participants who experience increases in psychiatric symptoms during the study. We will ask participants to sign a medical release form that will allow us to inform their psychiatrist or other healthcare provider that they are participating in a research study in which they may be receiving VAR under double-blind conditions.

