- 5) Pregnancy: If participant indicates she is pregnant or has a positive pregnancy test at any session, she will be withdrawn from the study, and this event will remain open until delivery. At that time the medical monitor will contact the participant to ask a few questions about the baby's health and will update the open 'Medical Event Form'.

The following will be monitored and can lead to the participant being withdrawn by the PI or medical monitor:

- 1) Any hospitalization or debilitation in which participation in the study could be detrimental to the recovery process. This will be self-reported by the participant and will be reviewed by the PI and medical monitor to determine whether continued participation in the study is appropriate.
- 2) If a participant is behaving in an inappropriate or threatening manner, admits to lying about eligibility criteria, including omitting previous medical diagnoses and medications, is participating in other research studies that could affect the primary outcome measures, or does not follow study instructions, then the PI can withdraw him or her at the PI's discretion.

Serious adverse events (SAEs): Information about all serious adverse events will be collected and recorded on a standard Serious Adverse Event Report Form. A serious adverse event is an undesirable sign, symptom or medical condition which:

1. is fatal or life-threatening
2. requires or prolongs hospitalization
3. results in persistent or significant disability/incapacity
4. constitutes a congenital anomaly or a birth defect
5. is medically significant, in that it may jeopardize the subject and may require medical or surgical intervention to prevent one of the outcomes listed above.

A hospitalization would not be considered to be a serious adverse event if it is for the routine treatment or monitoring of the studied indication (smoking), not associated with any deterioration in condition, is treatment, which was elective or pre-planned, for a pre-existing condition unrelated to the indication under study and did not worsen, is admission to a hospital or other institution for general care, not associated with any deterioration in condition, is treatment on an emergency, outpatient basis for an event not fulfilling any of the definitions of serious given above, and not resulting in hospital admission.

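### The PI is to create the randomization table, apparently with drug names, in a trial described as double-blind, and no safeguard keeps the code key from the PI

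*Combined protocol and SAP*

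**What the plan says.** The allocation procedure is in the Quality Assurance section, under the procedures for validity and integrity of the data. It states "A medication randomization table will be created by the PI" and continues: "The Research Assistant will be provided with a copy that has letter codes (A, B, C, or D) instead of medication names". The Research Assistant enters each new participant on a row of the table, copies that row's letter to the enrollment form and takes the pack with that letter. The packs carry the participant's ID and the letter code. A copy of the table then goes to the Data Manager.

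The same section says that one person, whose name is removed from the public text, "will remain blind to medication condition during each phase (R21 phase, R33 phase", and then: "The Data Manager will break the blind for [name] at the end of each phase". A separate sentence has the Data Manager break the blind for the medical monitor when an adverse event needs medical intervention. Under Potential risks of participation, item 5, participants' healthcare providers are to be told that "they may be receiving VAR under double-blind conditions".

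On the PI's other duties, the Quality Assurance section says "The PI will train and closely monitor the Research Assistant on the procedures to be used in this study". It adds meetings at least weekly and a PI review of each binder once that participant has finished. Under Collection and reporting of AEs and SAEs, participants who behave inappropriately, misreport eligibility, join other studies that could affect the primary outcomes or do not follow instructions may be removed: "then the PI can withdraw him or her at the" PI's own discretion.

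**The concern.** A copy that shows letters in place of drug names makes sense only if the original shows the names. The person who makes that original would then know what each letter means and could decode any participant whose letter came into view, on a form, on a pack or in the returned table.

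That person is also the PI, who oversees the staff member running the visits and makes some withdrawal decisions alone. Whether someone has failed to follow instructions is a matter of judgement. If allocation is known when that judgement is made, retention can come to differ between arms for reasons unrelated to treatment, and no later analysis can restore the blind. In R21 the stakes include the go/no-go decision. The rule can be met on either the primary or the secondary targets, and the CEQ scales that form the secondary targets are measured for this purpose at Session 8.

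**Working it through.** No sample size, power or error-rate figure is in question, so the check is a comparison of the relevant passages, followed by one labelled illustration.

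**1. Does the PI's table show drug names?** The plan does not say so directly. The contrast with the Research Assistant's coded copy implies it. Nothing says that the PI prepares only a coded list, passes the key to someone else or is shielded from it.

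**2. Does the blinding sentence settle the PI's status?** There are two cases.
- The removed name is the PI. The author of the table is then said to be blind with no mechanism given, and the section contradicts itself.
- The removed name is someone else. The PI's blinding status is then not stated anywhere.

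The same safeguard is missing in both cases, so the point does not depend on whose name was removed.

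**3. Can the key be linked to individuals?** Yes, through letters on the enrollment form, the packs and the completed table. The plan does not say whether the enrollment form is kept in the binder that the PI reviews. That review also comes after the participant has finished, so it bears less on that participant's retention than the weekly meetings do.

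**4. Which analyses are exposed?** These entries come from the Data Analysis Plan.

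| Analysis | Effect of a withdrawal before Session 8 |
|---|---|
| R21 QSU and MNWS negative affect (GEE, Sessions 2-8) | Earlier visits stay in the model |
| R21 CEQ scales (2 x 2 ANOVA, Sessions 1 and 8) | No Session 8 value, so no paired contribution |
| R21 relapse latency (t-test, clock starts at Session 8) | No latency observed |

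In R33 there is no Session 8 analysis of this kind. All randomized participants are included, with baseline values standing in for missing ones. A withdrawal there changes what is recorded for a person but does not remove that person.

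**5. Hypothetical worst case for the Session 8 analyses.** Assumptions: 48 / 2 = 24 per arm, normal outcomes, exactly the k most extreme participants in one arm lost, and all their data lost. The shift in that arm's mean is the sum of the expected k largest values divided by (24 - k). For 24 standard normal values, the expected largest is 1.948 and the second largest 1.503.
- k = 1: 1.948 / 23 = 0.085 SD
- k = 2: (1.948 + 1.503) / 22 = 0.157 SD

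Against the planned d = .40, these are 0.085 / 0.40 = 21% and 0.157 / 0.40 = 39%. They show how sensitive an arm of 24 is to a few selective losses. They do not predict what would happen.

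**The case against.** The strongest objection is that a reader might infer that the PI is unblinded from the start, and the documents do not establish this. No sentence says so. The person who stays blind may well be the PI, since the medical monitor is dealt with in a separate sentence. The removed name prevents a decision and is not itself a fault of the plan. This stands, and the point is therefore limited to an apparent key-holder with no described safeguard.

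Three further limits also stand.
- A reader might infer that the PI supervises the ratings. The plan has participants complete the repeated questionnaires, with the QSU as its example, and CO is a biochemical reading. Capsules and packs look identical, and the Research Assistant works from letters. Any influence on self-reports would have to pass through a Research Assistant who is meant to be blind.
- A reader might infer that the PI decides withdrawals in general. Several events require immediate withdrawal. Hospitalization or debilitation is reviewed with the medical monitor, and safety discontinuation rests with the medical monitor, the PI or both. Sole discretion covers only the conduct-related list.
- The 0.16 SD shift assumes a perfectly selective loss of the most extreme outcomes in one arm. Nothing in the documents suggests that this would occur, and the GEE and the R33 analysis do not behave that way.

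It can also be said that the Data Manager already breaks the blind, so part of the remedy exists. That is true of unblinding. It does not change who generates the table or who may see the key before then.

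**Conclusion.** The concern holds in limited form. As written, the plan has the PI create a table that appears to link codes to drugs, calls the trial double-blind and describes nothing that separates the table's author from the key. The conclusion rests on the natural reading of the sentence about the Research Assistant's copy, and it stands whether or not the removed name is the PI's.

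The procedure covers both phases (48 randomized participants planned in each), but that counts those under the procedure and does not measure bias. The practical exposure is retention and visit handling through the PI's oversight and sole-discretion withdrawals. It falls mainly on the R21 CEQ and relapse-latency analyses. Its size cannot be estimated from the documents; the 0.085 and 0.157 SD figures are hypothetical worst cases. The documents do not show that the PI is in fact unblinded or that any bias has arisen. The change should be made before randomization in the phase concerned, because a lost blind cannot be recovered.

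**What to change.** Replace the sentence that assigns the table to the PI. Have the compounding pharmacist or the Data Manager generate the table and hold the key linking letter codes to drug. The pharmacist prepares both products, and the Data Manager already performs the unblinding. State by role that the PI, the co-investigators and the Research Assistant do not see the key until the data for that phase are locked, and keep the existing emergency unblinding for the medical monitor. This also resolves the possible contradiction with the sentence on who stays blind.

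The same text should say how a table filled row by row carries out the allocation method given in the Brief Description of Protocol, "using urn randomization to stratify on gender and dependence", since under an urn scheme the assignment probabilities depend on earlier allocations within strata.

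The cost is one or two sentences and the reassignment of one task to existing staff. Sample size, visits and analyses do not change.

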SS will be randomized to one of 3 conditions for a 5-week period: (1) VAR plus a mobile CM intervention, (2) VAR plus a non-contingent reinforcement (NR) control condition, and (3) PLA plus the NR condition. During the first week, participants will undergo a standard 7-day medication (VAR or PLA) dose run-up period and will receive voucher-based reinforcement for texting videos of themselves providing CO samples twice per day, regardless of CO level. In Weeks 2-5, participants will continue to text video samples twice per day and will receive voucher reinforcement that is either contingent upon abstinence, or contingent only upon submitting the video (NR). Participants will visit the laboratory each week to complete assessments of smoking, craving, withdrawal symptoms, mood, subjective effects of smoking and psychiatric symptoms. They will also complete the CPT, cognitive battery, measures of quit interest, and provide a saliva sample for cotinine analysis at the beginning and end of the intervention period. At the end of the intervention, participants will be provided with brief advice to quit smoking and will be offered referrals to community treatments. They will also be administered a debriefing questionnaire in which they are asked to guess their medication condition and asked about the intervention acceptability, their willingness to participate in longer CM trials, and their willingness to receive prize-based incentives rather than vouchers.

Two weeks after Session 6, participants will be contacted by phone and asked about the frequency and quantity of cigarette and other nicotine/tobacco product use since the end of the active treatment period. Those indicating that they have been abstinent in the last 7 days will be provided with taxi transportation and compensation to provide CO verification of abstinence. Participants will be asked whether they have contacted and attended any community cessation treatments, and about their current interest in treatment. Participants will again be offered referrals to cessation treatments in the community. This assessment, including CO verification of abstinence, will be repeated 2 weeks later.

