A total of 48 randomized participants are planned for the R21 phase. This sample size is based on Aim 1, which is to determine effects of VAR versus PLA on smoking urges and negative affect during abstinence, reinforcing effects of a smoking lapse, cognitive function and time to relapse in SS. A repeated-measures design with 48 total participants provides 80% power to detect main and interaction effects on the primary targets (smoking urges and negative affect during abstinence) and secondary targets (reinforcing effects of a smoking lapse) of at least $d = .40$ in size, assuming a moderate within-subject autocorrelation. While this effect size is somewhat smaller than those detected by West et al. (2008) for effects of abstinence on urges and negative affect during abstinence and smoking satisfaction and reward from relapse (d 's = .32-.44), abstinence was not controlled or biochemically verified after target quit date in that study, and, as the authors noted, it is possible that the effects that they observed were due only to those who were completely abstinent. With our rigorous control of abstinence, which includes twice-daily CO testing and a stringent abstinence criterion, we believe that we will detect smaller effects. We are not determining sample size based on Aim 2 (which is to examine the extent to which the effects of VAR on time to relapse are mediated through its effects on the target mechanisms), but we should be able to

detect medium-sized group effects on latency to second lapse, and estimate the size of mediation relationships that would be detectable as significant. We anticipate 20% attrition between enrollment and randomization. Therefore, we anticipate needing to enroll up to 60 participants (30 per group) to include 48 in the intent-to-treat sample.

R33 phase:

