A total of 48 randomized participants are planned for the R33 phase. With 20% attrition estimated between enrollment and randomization, we anticipate needing to enroll up to 60 participants (20 per group) to include 48 in the intent-to-treat sample. Given that the PAR-14-230 funding announcement indicates that Stage 1B pilot studies funded through this R33 mechanism “are not expected to have sufficient power to conduct a strong test of efficacy”, we have not attempted to power this study to detect significant differences among the groups. We will focus on determining the feasibility and initial efficacy (i.e., effect sizes) of this intervention to determine if a larger-scale trial is warranted.

Trial Management

List of Participating Sites:

Brown University

Projected Timetable

Recruitment (cumulative)

R21 phase:

Year 1: 24 participants

Year 2: 48 participants

R33 phase:

Year 3: 16 participants

Year 4: 32 participants

Year 5: 48 participants

Target Population Distribution (e.g., women, minorities, etc.)

Age Range: Participants will be 18-65 years of age. Those under 18 will be excluded because the efficacy and safety of VAR in children has not been established.

Gender: Both men and women will be included. About 60% male participants are anticipated because schizophrenia is more prevalent among men (Aleman et al., 2003).

Racial and ethnic groups: Ethnicity/race will not be a selection/exclusion factor for study participation. Based on census data and our recent studies, we anticipate that 75% of participants will be Caucasian, 20% African American or multiracial, 4% Asian, 1% Native American and 15% Hispanic.

Data Management and Analysis

Data Entry, Acquisition and Transmission

Data will be entered directly by the participant or by the Research Assistant. Research materials include paper or computer-administered (Qualtrics or REDCap) questionnaires and tasks, structured clinical interviews, videos of participants providing a breath CO sample, breath samples for analyzing carbon monoxide and alcohol levels, saliva samples for analyzing cotinine, and urine samples for assessing tobacco toxicity biomarkers, illicit drug use and pregnancy.

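### Four reusable letter codes and a list held by the enrolling Research Assistant mean that one known or guessed code exposes about 12 R21 participants instead of one

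*Combined protocol and SAP*

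**What the plan says.** The procedure is in the combined protocol and SAP under Quality Assurance, in the text on validity and integrity of the data. The PI creates the medication randomization table. The Research Assistant's copy of it shows "letter codes (A, B, C, or D) instead of medication names". On enrolling someone, the Research Assistant writes the name and ID on a row, records that row's letter and takes a pack bearing that letter. The blister packs show the study ID and the letter. A copy of the table then goes to the Data Manager. The same section has the Data Manager unblind the medical monitor when an adverse event needs medical care.

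On numbers, Power Calculation and Sample Size states: "A total of 48 randomized participants are planned for the R21 phase", and for the second phase: "A total of 48 randomized participants are planned for the R33 phase". On side effects, the varenicline entry under Potential risks of participation gives "mild to moderate nausea, occurring in 25-45% of users". Adverse events are collected weekly with a checklist and open questions.

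No section describes unique kit numbers, masking of later rows, release of one assignment at a time, or a step that keeps one unblinding from exposing others on the same letter.

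**The concern.** A code that many participants share is only as safe as its weakest disclosure. There are two routes to it. The first is logical: whoever knows one participant's arm and can see letters knows the arm of the whole letter group. The second is statistical: a side effect that says little about one person says much more when added up over a group known to be on the same drug.

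The list adds a third issue. The row letters are already in the table when a participant is entered, and nothing says later rows are hidden. If a letter has been decoded, the person enrolling may know the next assignment in advance.

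The Research Assistant explains the repeated questionnaires, answers questions about them and checks them for completeness. The Questionnaire on Smoking Urges and the withdrawal scale's negative affect score are the primary targets, and the go/no-go decision for R33 rests on the primary or secondary targets. A staff member who suspects the arm could influence those subjective scores or the order of enrolment.

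**Working it through.** **Inputs from the documents.** 48 randomized in each phase; 20% attrition before randomization; two R21 arms of equal size ("we anticipate needing to enroll up to 60 participants (30 per group"); three R33 arms, two of them on varenicline; four letters; varenicline nausea 25-45%.

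**Assumed, because the documents are silent.** Letters used equally; two letters per drug; placebo nausea 5-20%, with 10% as the central value. The central varenicline rate of 35% is the midpoint of the plan's range.

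**1. The plan's own figure.** 48 / (1 - 0.20) = 60 enrolled, as stated. The 48 can be used as the base.

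**2. Participants per code.**
- R21: 48 / 4 = 12. If each letter were instead drawn independently with probability 1/4, the SD would be sqrt(48 x 0.25 x 0.75) = 3, and the 95% range 6 to 18.
- R33 with equal groups: 48 / 3 = 16 per group, so 32 on varenicline and 16 on placebo. Two letters each gives 16 per varenicline letter and 8 per placebo letter. Three and one gives 32 / 3 = 10.7 and 16.

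One known arm therefore discloses about 12 people in R21 (the index case and about 11 others), and roughly 8 to 16 in R33 under these splits. A unique code discloses one.

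**3. Decoding by pooled nausea.** With n participants per letter, let V be the nausea count on a drug letter and M the larger of the two placebo-letter counts. Both drug letters exceed both placebo letters with probability

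P = sum over m of P(M = m) x P(V > m)^2.

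Worked for n = 3, 35% v 10%:
- P(M = 0) = 0.729^2 = 0.5314; P(M = 1) = 0.972^2 - 0.5314 = 0.4134; P(M = 2) = 0.999^2 - 0.972^2 = 0.0532.
- P(V > 0) = 0.7254; P(V > 1) = 0.2818; P(V > 2) = 0.0429.
- P = 0.5314 x 0.5262 + 0.4134 x 0.0794 + 0.0532 x 0.0018 = 0.3125.

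The same formula at 35% v 10%:

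| Per letter | Total randomized | P |
|---|---|---|
| 2 | 8 | 22% |
| 3 | 12 | 31% |
| 4 | 16 | 38% |
| 6 | 24 | 50% |
| 12 | 48 | 74% |

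At 12 per letter over the range of rates:

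| Varenicline v placebo | P |
|---|---|
| 25% v 20% | 19% |
| 35% v 20% | 42% |
| 25% v 15% | 31% |
| 35% v 10% | 74% |
| 45% v 5% | 96.5% |

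A blind choice of two letters out of four is right 1 time in 6 (17%). P counts any tie as a failure, so it is conservative beside that benchmark. With ties broken at random (simulation, 200,000 draws), the two highest letters are both drug letters in 81% of draws at 35% v 10%, 27% at 25% v 20% and 98% at 45% v 5%.

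**4. What sharing the code adds.** Judging each person by their own nausea alone, the proportion classified correctly at 35% v 10% is 0.5 x 0.35 + 0.5 x 0.90 = 62.5%. Pooling over 12 per letter, it is 90%. Over the assumed range the figures are 52.5-70% individually and 59-99% pooled.

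**The case against.** A reader might infer that one emergency unblinding breaks the Research Assistant's blind. The documents do not support that: the Data Manager informs the medical monitor, and no section passes the arm on. The exposure is to anyone who both learns an arm and can see letters, which includes the Research Assistant only if told.

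A reader might also infer that side effects reveal the arms. They make them likelier, no more. The 74% belongs to a completed phase, when nobody remains to be enrolled. Only the smaller-group figures bear on concealment, such as 50% at 6 per letter, which is 24 randomized and the cumulative R21 target for Year 1. Placebo nausea and the letter-to-drug split are not in the documents, the sorting rule presumes the observer knows the split is two and two, and at 25% v 20% the result is close to a guess.

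The Research Assistant's part in adverse-event collection and in coding the CO videos is likewise an inference. The plan describes collection in the passive voice, speaks of an interviewer, and does not say who codes the videos.

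Finally, it would be too strong to say that blinding and concealment are removed for the go/no-go outcomes. Participants complete the repeated scales themselves and take look-alike capsules, so staff influence is indirect. Four codes also disclose fewer people per code than two would.

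All of this limits the size of the effect. It does not touch the procedure itself: the letters are shared, the enrolling person holds the list, and nothing else in the plan compensates.

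**Conclusion.** The concern holds as a weakness of the blinding and concealment procedure that is cheap to remove. The firm part needs no side-effect rates: one arm learned, together with sight of the letters, fixes the arm of about 12 R21 participants, assuming equal use of the letters; R33 may differ. The probabilistic part rests on assumed placebo nausea and an assumed two-and-two split. It gives 31% at 3 per letter, 50% at 6 and 74% at 12 in the central case, with a range at 12 of 19% to 96.5%. Weaker concealment follows only if later rows are visible and a letter has been decoded. The documents do not show that any blind has been or would be broken. They show that the blind of the person who explains and reviews the self-completed scales is less well protected than it could be.

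**What to change.** Drop the letter codes. Label each blister pack only with the participant's study ID, which it already carries, or with a unique kit number. Keep the table with the Data Manager, who releases one assignment at a time after enrolment, and do not give the Research Assistant a copy. Release in sequence also suits the urn randomization named in the Brief Description of Protocol, where each assignment depends on those before it.

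The cost is a change to pack labelling and a few sentences in Quality Assurance. The pharmacist must prepare packs by participant or kit number instead of by letter. The change does not stop guessing from a person's own side effects (62.5% correct in the central case, where a coin toss gives 50%), but there is no longer a letter group to pool, and one disclosure stays with one participant.
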